DigiPrEP Statistical Analysis Plan

Official title: Feasibility and Acceptability of Digital Pills to Monitor PrEP Adherence in MSM With Substance Use

NCT number: NCT03842436

Document date: September 03, 2021

DigiPrEP Statistical Analysis Plan

Sociodemographics.

Descriptive statistics were calculated for selected variables.

Digital pill system (DPS) performance and engagement metrics.

To analyze the performance of the DPS, the ground truth of PrEP ingestion events were defined as the pill counts obtained each month (i.e., the number of unused pills returned, subtracted from the number of pills previously dispensed). The number of DPS-recorded ingestions – which included the number of both Reader-detected and manually-reported ingestions – was compared with the aggregate pill count at each monthly timepoint; this was defined as the overall performance metric for the DPS. The Reader-detected ingestions count was used to reflect the number of times the DPS was operated correctly. Successful DPS operation was defined as ingestion of a digital pill, proper use of the wearable Reader, and confirmation of the ingestion on both the Reader and the app.

Reader-detected ingestions and manually-reported ingestions that co-occurred within 30 minutes were identified and reconciled; these events likely represented episodes in which a digital pill was ingested, and the ingestion was detected by the Reader, but the participant elected to manually record the ingestion in-app because the Reader was not correctly paired to the smartphone or was delayed in detecting the ingestion. Additionally, several ingestions were manually reported due to a known programming error in the app early in the study. As such, two participants were instructed to manually log all ingestions until an app update was made available; ingestion data for these two individuals were downloaded from their Readers at the end of the study period, and all Reader-detected ingestions were reconciled with manually-reported ingestions.

Participant engagement with the DPS was measured by calculating the total number of DPS-recorded ingestions and comparing the number of monthly DPS-recorded ingestions across each month of the study period.

TFV-DP in DBS.

We also compared drug concentrations of TFV-DP as measured in DBS at months one and three to DPS-recorded PrEP adherence. First, we identified all DBS samples that, as a result of scheduling challenges, were obtained more than five days after the conclusion of DPS-recorded ingestions, and excluded these DBS samples from analysis, as they resulted in incomplete data to compare with DPS-recorded ingestions. All other DBS samples were paired, based on their collection dates, with the corresponding average of DPS-detected ingestions during the three-week period prior to DBS collection. We dichotomized TFV-DP levels using a cutoff of ≥ 700 fmol/punch to indicate at least four doses of PrEP ingested per week.^{1,2} Using TFV-DP in DBS < 700 vs ≥ 700 fmol/punch as a dichotomous variable, and considering the granular continuous adherence data from the digital pill, we then calculated a point biserial correlation between TFV-DP in DBS and digital pill adherence. Finally, we analyzed the paired TFV-DP concentrations and DPS-recorded adherence data at months one and three, and calculated Pearson's correlation coefficients for each independent timepoint. Analyses were completed using SAS (version 9.4).³

Qualitative analyses.

Qualitative user experience interviews were transcribed and coded using applied thematic analysis.^{4,5} A codebook was generated. All interviews will then double-coded by two study team members; coding was paused and evaluated every five transcripts to ensure consistency and to resolve and document any discrepancies. A kappa statistic was calculated, utilizing a cutoff of > 0.8 to ensure interrater reliability between coders. Coders reviewed aggregate coding to identify and discuss final

themes surrounding user experiences, which were reviewed by the study team as a whole. Qualitative analyses were facilitated by NVivo software.⁶

References

3. SAS Institute Inc. *SAS.*; 2013.

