**Aim 2 – Study Visit 2:** We will contact participants on days 23, 25, and 29 to remind participants of their Study Visit 2 appointment. During this study visit, participants will have blood drawn via phlebotomy and placed on a blood spot card in order to assess PrEP adherence. De-identified specimens will be banked for future use in drug abuse screening. We will review digital pill adherence data with participants in Nomi and conduct a pill count to validate adherence data from the digital pill and Reader. We will review discordant counts, periods of Reader activity that suggest no use of the Reader device, and digital pill use with the participant. We will additionally review any potential nonadherent events detected by the digital pill with participants using timeline followback to gauge potential reasons for nonadherence. We will view the adherence interface with study participants and discuss events surrounding potential nonadherence events. We will record user responses to

each of these timeline followback events. We will also dispense an additional 30-day supply of digital pills to participants. We will schedule participants for Study Visit 3 prior to discharge, which will occur a maximum of 30 days (i.e., 23-30 days) after Study Visit 2. Participants will be reminded that we will pass their adherence data along to their PCP; participants will have the option of opting out of this mechanism at each study visit. At the end of Study Visit 2, the participant will be remunerated via a \$25 check.

**Aim 2 – Study Visit 3:** We will contact participants on days 53, 55, and 59 to remind them of their Study Visit 3 appointment. During this visit, we will review adherence data from the digital pill in Nomi, conduct pill counts with participants, address discordant counts and review reader activity with the participants and address any nonadherence events potentially linked to sexual activity or substance use. The participant will receive a final 30 day refill of digital pills and will be remunerated via a \$50 check.

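### The only stated agreement with pill counts mixes manual reports with Reader detections; the Reader-only ratio should be reported beside it

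*SAP*

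**What the plan says.** In the SAP section on digital pill system (DPS) performance and engagement metrics, the reference is the monthly pill count: pills dispensed minus unused pills returned. The DPS-recorded total "included the number of both Reader-detected and manually-reported ingestions", and this total "was compared with the aggregate pill count at each monthly timepoint". The SAP names that comparison its overall performance metric.

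The Reader-only number has a different use: "The Reader-detected ingestions count was used to reflect the number of times the DPS was operated correctly". No denominator or reference is given for it. The next sentence defines successful operation and adds a condition, namely "confirmation of the ingestion on both the Reader and the app".

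The section then describes how overlapping records were handled. Reader and manual records within 30 minutes of each other were reconciled. The SAP's likely explanation is that the participant chose to "manually record the ingestion in-app because the Reader was not correctly paired to the smartphone", or that the Reader was slow to detect the dose. Two participants logged by hand because of an early app fault; "ingestion data for these two individuals were downloaded from their Readers at the end of the study period". Their Reader detections were then matched against the entries they had typed in.

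The protocol's purpose for pill counts is narrower. At Study Visit 2 (Section V) staff are to "conduct a pill count to validate adherence data from the digital pill and Reader". Section VI, under Aim 2, plans to calculate how accurate the digital pill is against pill counts, and Section IX repeats this. The protocol expects manual entries (Participant messaging in Section V; Data Entry Process in Section IX) but does not say whether they belong in the accuracy figure.

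**The concern.** A manual entry is self-report, and the trial is a proof of concept for a system meant to sense ingestion directly. If a dose the Reader missed is typed into the app, the composite counts it as a success. The composite therefore describes how completely doses were recorded by any route. Alone, it does not show how many were sensed.

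Agreement with pill counts is a stated Aim 2 output. If only the composite is reported against pill counts, it may be taken as the accuracy of the pill and Reader, which is what the protocol said it would measure. The study is descriptive, with no accuracy target and no decision rule, so what is at stake is the conclusion about detection.

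The secondary issue is one of definition. Two adjacent sentences describe correct operation with different requirements, and the same section describes events that may meet one and not the other.

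**Working it through.** The plan states no accuracy figure, so there is nothing to reproduce. The check is algebra followed by illustration.

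**Notation.** P is the number of doses by pill count, R the number of Reader-detected doses, and M the number of manual-only reports left after reconciliation. The SAP does not say what form its comparison takes; I take it as a ratio.

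- Composite: (R + M)/P
- Reader-only: R/P
- Difference: M/P

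The difference is an identity and needs no assumption. The documents give none of R, M or P.

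**Illustration.** Let r = R/P, and let f be the share of Reader misses that were logged by hand, assuming no false entries and no duplicates left over. The composite is then r + f(1 − r). Both r and f are assumed.

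| Reader-only r | f = 0 | f = 0.5 | f = 1 |
|---|---|---|---|
| 60% | 60% | 80% | 100% |
| 70% | 70% | 85% | 100% |
| 80% | 80% | 90% | 100% |
| 90% | 90% | 95% | 100% |
| 95% | 95% | 97.5% | 100% |

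Over this grid the gap runs from 0 to 40 percentage points.

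**In doses.** The protocol plans 15 participants (Section II) with 90 pills each (Drug procurement, Section V): 15 × 90 = 1,350 if all complete and take every pill. With r = 80%, R = 0.80 × 1,350 = 1,080, leaving 270 misses. With f = 0.5, M = 135, so the composite is 1,080 + 135 = 1,215, and 1,215/1,350 = 90%.

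**Reading back from a composite of 95%.** The share of misses that must have been logged is f = 1 − 0.05/(1 − r). For r = 90% this is 1 − 0.05/0.10 = 0.50; for r = 80%, 1 − 0.05/0.20 = 0.75; for r = 50%, 1 − 0.05/0.50 = 0.90. The same composite fits very different sensor performance, but a large gap requires that most misses were logged.

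**Operation count.** The two participants with the app fault could hold at most 2 × 90 = 180 of 1,350 planned doses (13.3%). That ceiling supposes they were affected for all 90 days. The SAP places the fault early in the study, speaks of several ingestions, and says manual logging stopped once an update was available. An assumed 7 days would give 2 × 7 = 14 doses (1.0%). The number of unpaired-Reader events in other participants is not given.

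**The case against.** The strongest reply is that nothing is hidden or lost. The SAP says what the composite contains, calls it an overall metric rather than sensor accuracy, reconciles near-simultaneous records and keeps the Reader-detected count. The app is part of the system on which participants are trained at Study Visit 1, and manual recording is one of its functions, so a whole-system metric is a fair choice. Detection failures are also followed up: the protocol provides for review of discordant counts and of periods without Reader use, annotation of transmission errors, and an audit trail of edits.

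Most of this stands. A reader might infer that sensed and typed doses cannot be told apart. The documents do not support that, because composite minus Reader-detected gives the manual-only entries, and Reader-detected over pill count gives capture. A reader might also infer that performance is materially overstated, but the documents give no counts from which to say so. What remains is that the one comparison actually written uses the composite, while the protocol promised validation of the pill and Reader. Visit-level review does not supply the missing summary figure.

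On the operation count, there are harmless readings. The Reader count may be meant only as a proxy. A delayed detection may later have been confirmed on both devices. A manual in-app entry may itself count as app confirmation. The SAP adopts none of these explicitly, so this is a wording mismatch, not a demonstrated misclassification.

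**Conclusion.** The point holds in a limited form and is worth fixing. The SAP states no Reader-only comparison with pill counts, and its only stated agreement figure exceeds that ratio by M/P, the manual-only share of pill-count doses. The true size is unknown and could be small; the 0 to 40 point range rests on assumed Reader capture of 60% to 95% and any degree of manual logging. The 13.3% for the two participants is a ceiling that the SAP's own description makes unlikely, and should not be read as an estimate.

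The mismatch between the operation count and the definition of successful operation is minor. Rerunning the analysis without the two participants is not needed for the Reader-only ratio: the fault was in the app, and their Reader data were recovered by download.

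**What to change.** 1. At each monthly timepoint, report Reader-detected ingestions divided by pill count. Label it Reader-detected capture under field use, because it includes periods when the Reader was not being used and is therefore not a pure measure of sensor failure.
2. Keep the composite beside it, labelled system with manual back-up.
3. Align the wording of the correct-operation count with the definition of successful operation, and state how events with an unpaired Reader and those downloaded at the end of the study are classed.

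The cost is some SAP wording and one extra ratio from counts the SAP already uses; no new data are needed. The downside is that the Reader-only figure will probably be lower than the composite.

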**Aim 2 – Study Visit 1:** During Study Visit 1, participants will complete a baseline self-report questionnaire, and the study team will conduct a short training around operation of the digital pill system (i.e., digital pills, Reader device, and mobile application) and instruct participants on basic troubleshooting of the technology. We will also help participants to download the mobile application where their adherence data will be recorded and accessible, train them on how to use the app, and register them on the collaborator interfaces (iAssist and Nomi). Participants will be provided with a 30-day supply of digital PrEP (Truvada); participants will then ingest their first digital PrEP dose during the visit to demonstrate their understanding of how to operate the digital pill system and to ensure the technology is functioning properly. Participants will receive a brief reference guide (see *refguide*) with key contact information and basic information regarding the digital pill and Reader. Participants will be scheduled for Study Visit 2, which will occur a maximum of 30 days (i.e., 23-30 days) after Study Visit 1, in order to ensure that participants do not run out of digital pills prior to receiving a refill. We will contact study participants via text message on days 1, 2, 5, and 7 to ensure technology is functioning. Additionally, beginning one week after Study Visit 1, participants will receive brief weekly surveys through the Nomi interface asking them to self-report substance use and sexual activity (see *DigiPrEP Study Messages\_Participant Only*). At the end of Study Visit 1, participants will be remunerated via a \$25 check.

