## VI. Biostatistical Analysis

Aim 1: We will conduct qualitative analysis on individual interviews in aim 1 to elucidate themes of technology acceptance, design, and optimal timing and delivery of messaging.

Aim 2: We will calculate descriptive statistics regarding the degree of adherence collected from the digital pill. We will also calculate the accuracy of the digital pill in comparison to pill counts and validate ingestion data compared to dried blood spot data. Because this is a pilot, proof-of-concept study, we will not be powered to determine the degree of adherence the use of a digital pill alone confers upon study participants.

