## **IX. Data Monitoring and Quality Assurance**

We will review and monitor data from DigiPrEP for each study participant. At each study visit, participants will undergo pill counts to correlate adherence data from DigiPrEP, and calculate the accuracy of the digital pill to measure PrEP adherence. Any discrepancies between the digital pill and pill counts will be addressed in real time at each study visit with the participant. For each participant, we will also review signaling from the digital pill to the Reader with our industry collaborator (eTectRx) to ensure there are no errors in data transmission contribution to missed adherence events. If errors occur as a result of data transmission, we will annotate this on the ingestion data.

The study investigators will conduct QA to review data after half of the patients (N=7) of Aim 2/3 are enrolled to ensure that data is accurate and no errors have been made.

The principal investigator ([name]) will be responsible for monitoring adverse events during the study, but Drs. [name] and [name] will assume this responsibility in the event that [name] is unavailable. The role of the responsible person is 1) to identify the concern, 2) develop an appropriate response that involves consultation whenever possible to alleviate or minimize any adverse event, and 3) to ensure that the adverse event is reported in a timely manner to the responsible authority.

Participants will be monitored for occurrence of events defined as any undesirable experience or unanticipated benefit. Events may occur during recruitment, technology deployment, and qualitative interviewing. For example, a participant may become distressed when asked questions about substance abuse and its impact on PrEP adherence. Based upon previous research couched in technology among hidden populations, we anticipate that these effects will be minimal. The principal investigator will assess whether an undesirable experience occurred (adverse event) and will record details of all adverse events (death, life threatening illness, new serious or permanent disability) that occur. Should such an event occur, the principal investigator will report the event within 24 hours to the Fenway Institute IRB.

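### The overall performance metric compares total digital pill records with an aggregate pill count, so errors in opposite directions can offset, and no participant-level agreement is specified

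*SAP*

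**What the plan says.** The SAP section on DPS performance and engagement metrics takes the pill count as the reference: "the ground truth of PrEP ingestion events were defined as the pill counts obtained each month". The quantity tested against it is the number of DPS-recorded ingestions, "which included the number of both Reader-detected and manually-reported ingestions". That number "was compared with the aggregate pill count at each monthly timepoint; this was defined as the overall performance metric for the DPS". The SAP does not say what the aggregate is taken over, or whether the comparison is a ratio, a difference or something else.

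Two further provisions bear on the count:

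- **Double records.** "Reader-detected ingestions and manually-reported ingestions that co-occurred within 30 minutes were identified and reconciled". For two participants told to log every dose by hand, all Reader data were downloaded at the end and reconciled with the manual entries.
- **A Reader-only count.** "The Reader-detected ingestions count was used to reflect the number of times the DPS was operated correctly". No statistic of agreement with pill counts is attached to it.

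The protocol leaves the method open. Section VI says "We will also calculate the accuracy of the digital pill in comparison to pill counts", and section IX says that pill counts at each visit will be used to "calculate the accuracy of the digital pill to measure PrEP adherence". Neither names a unit of analysis or a statistic.

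**The concern.** A comparison of totals answers whether, over everyone, the right number of records was produced. It does not show whether each man's record was right. If some records are surplus (a duplicate outside the 30-minute window, or a manual entry for a dose not taken), they fill the gap left by doses that went unrecorded elsewhere. The total can then look complete while individual totals are wrong. A shortfall concentrated in one or two men also looks the same as a small shortfall in everyone.

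The unit matters because the protocol uses the device one participant at a time. Under section V, pill counts are made for each man at Study Visits 2, 3 and 4, and discordant counts are reviewed with him. His adherence data go to his primary care physician if he agrees. Staff contact him after 48 hours (2 doses) without a detected ingestion, or after more than 2 missed doses in a week. Errors of a few doses in one man's record are therefore the errors of interest, and a pooled figure does not describe them.

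**Working it through.** **Inputs from the documents.** Planned Aim 2 sample of 15 (protocol section II). 30 pills dispensed per period and three pill counts per man (section V), so at most 15 × 3 = 45 participant-months. Neither document gives an accuracy target or result for this metric, so there is no stated figure to reproduce. All error patterns below are assumptions.

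**Notation.** For man *i* in one month, P is the pill count and D the DPS-recorded count after reconciliation.

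- Pooled ratio = ΣD / ΣP
- Absolute discrepancy = Σ|D − P| / ΣP

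**1. Offsetting between men.** Let P = 28 for all 15. Three men are over-recorded by 4, six are under-recorded by 2, and six are exact.

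- ΣP = 15 × 28 = 420; ΣD = 420 + 3×4 − 6×2 = 420; ratio 100%.
- Mean absolute difference = (12 + 12)/15 = 1.6 pills; 1.6/28 = 5.7%.
- Within ±1 pill: 6 of 15. Within ±2 pills: 12 of 15.

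A second pattern varies the size of the error. Let P = 24 (total 360), with seven men over by *e*, seven under by *e* and one exact. The ratio is 360/360 = 100% for every *e*. The absolute discrepancy is 14*e*/360: 7.8% for *e* = 2, 15.6% for *e* = 4, 23.3% for *e* = 6.

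**2. The same total from different patterns.** With P = 28, 13 men at 100% and 2 men at 25% give (13×28 + 2×7)/420 = 378/420 = 90%. A 10% shortfall in everyone gives the same 90%. In the first case 13 of 15 men agree exactly; in the second each is short by 2.8 pills on average. The mean absolute difference is also 2.8 in both (42/15), so only the numbers within ±1 and ±2 pills separate them.

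**3. How far this depends on over-recording.** Simulation with 15 men and 4,000 runs. Pills taken are binomial (30, 0.8). Each man's missed-record and extra-record rates are drawn from gamma distributions with shape 1 and the means shown.

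| Mean missed rate | Mean extra rate | Pooled ratio | Absolute discrepancy | Ingestions truly recorded |
|---|---|---|---|---|
| 5% | 0 | 95.0% | 5.0% | 95.0% |
| 5% | 5% | 100.0% | 6.4% | 95.0% |
| 10% | 0 | 90.0% | 10.0% | 90.0% |
| 10% | 5% | 95.0% | 9.7% | 90.0% |
| 10% | 10% | 100.1% | 11.7% | 90.1% |
| 20% | 0 | 80.1% | 19.9% | 80.1% |
| 20% | 20% | 100.0% | 21.3% | 80.1% |

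With no extra records, the pooled ratio equals the true recording rate. It becomes too favourable only as extra records appear.

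**4. Offsetting within one man's month.** If P = 24 and a man has *m* missed and *m* spurious records, then D = 24 and his difference is 0. The share of his ingestions recorded is (24 − *m*)/24: 95.8% for *m* = 1, 87.5% for *m* = 3, 79.2% for *m* = 5. Participant-month differences remove the offsetting between men but not this part. A monthly pill count carries no dates, so it cannot resolve it alone.

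**The case against.** - **The SAP does not say the count is pooled over men.** This is fair: pooling is the natural reading, not a stated fact. If *aggregate* means one man's monthly total, offsetting between men does not arise at that step. Offsetting within the month remains, and no participant-level summary is specified on either reading.
- **Over-recording is already controlled.** This is largely true. The SAP reconciles Reader and manual records within 30 minutes, and all Reader records for two participants. The protocol reviews discordant counts at visits (sections V and IX) and requires edits to be agreed, approved by the principal investigator and audited (section IX). The Reader-only count leaves out manual entries. These steps reduce surplus records. They give no rule for pairs further apart than 30 minutes, or for unverified manual entries in the other men, and they do not change how the overall metric is calculated.
- **The SAP has a paired analysis elsewhere.** The dried blood spot correlations pair each sample with that man's recorded doses. They compare records with drug level, and a correlation does not measure agreement with pill counts.
- **It is a 15-person pilot.** Section VI disclaims power for an effect on adherence, which is a different matter from describing how well the device records. The pilot setting does justify keeping the remedy descriptive.

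A reader might also infer that an interval will be computed as if about 1,350 pills were independent. The documents do not support this: the SAP plans no interval for this metric, and 1,350 is 15 × 90 pills dispensed, not ingested.

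**Conclusion.** The point holds as an inexpensive improvement to the analysis. On the natural reading, the overall metric allows over-recording and under-recording to offset, and neither document specifies a participant-level comparison with pill counts. In the examples, a pooled figure of 100% goes with absolute discrepancies of 5.7% to 23.3%. These sizes rest on assumed error patterns, several chosen to balance exactly, and show only what the metric can conceal.

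A reader might go on to infer that the reported performance is inflated. The documents do not support that: they give no count of surplus records, and without any there is nothing to offset. Nor does section IX of the protocol expressly ask for accuracy person by person. The case for the individual as the unit rests on how the counts are taken and how the adherence data are used.

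**What to change.** In the SAP section on DPS performance:

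1. Define *aggregate* and name the comparison statistic.
2. For each participant-month, calculate DPS-recorded minus pill-count doses. Report the signed mean, the mean absolute difference, and the numbers within ±1 and ±2 pills.
3. If limits of agreement or an interval are given, allow for up to three months per man, for example by resampling participants.
4. Show Reader-detected and manual-only records separately beside each pill count, because a net difference near zero can still hide missed and spurious records within the month.
5. Keep the aggregate comparison as a secondary summary.

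The cost is a few lines of SAP text and one extra table from data already held. The headline figure may look less favourable. As the SAP is written largely in the past tense, the table should be labelled as an addition.

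### The engagement metric is a raw count of recorded ingestions, so on its own it does not separate missed PrEP doses from non-use of the device, and it has no denominator

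*SAP*

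**What the plan says.** The SAP, under Digital pill system (DPS) performance and engagement metrics, defines engagement in one sentence: "Participant engagement with the DPS was measured by calculating the total number of DPS-recorded ingestions", together with "comparing the number of monthly DPS-recorded ingestions across each month of the study period". No denominator is given. A recorded ingestion is a composite, "which included the number of both Reader-detected and manually-reported ingestions".

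The same records also stand for adherence. Under TFV-DP in DBS, the SAP compares drug concentrations "to DPS-recorded PrEP adherence". Protocol section VI gives the Aim 2 output as: "We will calculate descriptive statistics regarding the degree of adherence collected from the digital pill".

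The SAP does have a separate measure of doses taken: "the ground truth of PrEP ingestion events were defined as the pill counts obtained each month". The recorded count "was compared with the aggregate pill count at each monthly timepoint; this was defined as the overall performance metric for the DPS". Reader-detected ingestions are counted separately, as an indicator of correct operation.

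Protocol section V (Aim 2, Study Visit 2) has staff go over with each participant "periods of Reader activity that suggest no use of the Reader device", along with discordant counts. Under Participant contact in the same section, a run of undetected doses triggers a call to find out whether the cause is an operating problem or true nonadherence. Section IX has transmission errors annotated on the ingestion data. The SAP does not say that any of this enters the engagement measure.

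**The concern.** The study asks whether men on PrEP will keep using a device that monitors PrEP. Skipping the medicine and not using the device are therefore different outcomes. A man who misses doses but uses the Reader for every dose he takes is a success for the device. A man who takes every dose and often leaves the Reader aside is a failure for it. A count of records falls by the same amount in both cases.

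Two features of the definition add to this:

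- **No denominator.** The count moves with the length of the visit interval as well as with behaviour.
- **Manual entries count.** A man who stops using the Reader but logs doses in the app still scores as fully engaged.

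A reader shown only the monthly engagement counts could take a decline as loss of interest in the device when it was missed PrEP or a short interval, or the reverse.

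**Working it through.** The plan states no figure for engagement, so there is nothing to reproduce. The check is whether the metric identifies the behaviour it is named for.

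**Inputs from the documents.** The visit interval is 23 to 30 days (Protocol V, Study Visit 1 and Study visit scheduling). Dosing is daily. The engagement metric is the recorded count R. Doses taken by pill count, T, is pills dispensed minus unused pills returned (SAP).

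**Assumed for illustration (not trial data).** A 30-day month (D = 30) in which each man has R = 20.

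**Step 1: same count, different behaviour.**

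| Case | R (engagement as defined) | T (pill count) | R/T (share of doses captured) | T/D (adherence) |
|---|---|---|---|---|
| A: doses missed, device always used | 20 | 20 | 20/20 = 100% | 20/30 = 67% |
| B: all doses taken, device not used for 10 | 20 | 30 | 20/30 = 67% | 30/30 = 100% |
| C: some of each | 20 | 25 | 20/25 = 80% | 25/30 = 83% |

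The metric is 20 in all three cases. Dividing R by days does not help, since 20/30 = 67% each time. R/T and T/D together separate them, and both come from quantities already collected.

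**Step 2: a trend.** Suppose R falls from 27 to 18 between two months of equal length. If T also goes from 27 to 18, R/T stays at 100% and the fall is all missed doses. If T stays at 27, R/T goes from 100% to 18/27 = 67% and the fall is all failure to record. The count alone does not choose between these; the pill counts do.

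**Step 3: interval length.** Take a month to be the interval between visits, which is how the pill counts are obtained. With perfect dosing and perfect recording, R = 23 over 23 days and R = 30 over 30 days. The fall from the longest to the shortest interval is 1 − 23/30 = 23.3%. Over three intervals, the total for a perfect user can lie anywhere from 3 × 23 = 69 to 3 × 30 = 90.

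**Step 4: pooling.** The SAP compares R with an aggregate pill count and does not say whether this is done per participant. If pooled, A and B together give (20 + 20)/(20 + 30) = 80%. Two men like C give (20 + 20)/(25 + 25) = 80%. A pooled ratio cannot show that one man accounts for all the unrecorded doses.

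**The case against.** The strongest reply is that the same SAP section already compares recorded ingestions with pill counts every month, and counts Reader-detected ingestions separately. Applied to cases A and B, that comparison gives 20 against 20 and 20 against 30. This is correct, and it limits the point. A reader might infer that the plan cannot tell missed PrEP from device abandonment, or that a monthly fall is uninterpretable. The documents do not support that: the data that separate the two are collected and partly tabulated. What stands is narrower. The comparison is labelled performance, is not stated to be per participant, and is not used to define or interpret engagement, which is still reported as a raw count.

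Three other inferences also go too far:

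- **That the SAP contains no adherence output.** Its DBS analysis forms an average of digital pill ingestions over the three weeks before each sample, and the monthly counts are themselves descriptive. What the SAP does not list is a monthly adherence summary with a stated denominator.
- **That participants were selected for irregular adherence.** The Aim 2 criteria in Protocol section III require substance use and current PrEP use; none concerns adherence.
- **That Reader-active days over days with pills in hand would be a better engagement measure.** The documents do not show that the Reader is worn on days without a dose, or that day-level logs can be exported. If a man who skips a dose also leaves the Reader off, A and B both score 20/30 again.

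It is also fair to say that this is a descriptive proof-of-concept study with N=15, with no test, threshold or go/no-go rule tied to engagement.

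**Conclusion.** The point holds in this limited form. The engagement metric, read alone, mixes missed doses with failure to record them. In the illustration, one value (20) covers adherence from 67% to 100% and capture from 100% down to 67%. Lacking a denominator, it can also fall by up to 23.3% with unchanged behaviour. That bound assumes that a month is a visit interval and that two intervals sit at opposite ends of the allowed range; intervals of similar length would give less. The 30-day cases are assumptions, not trial results.

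No error rate or sample size is affected. The consequence is that the engagement result, as defined, does not measure device use, although data already in hand would allow it to. For a feasibility study of a monitoring device, that is worth correcting.

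**What to change.** For each participant-month, report:

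1. Engagement: DPS-recorded ingestions divided by doses taken by pill count.
2. The same ratio with Reader-detected ingestions only, after the SAP's reconciliation, so that manual logging does not pass for Reader use.
3. Adherence: pill-count doses divided by days in the interval, with the rule for counting visit days stated.

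Compare these ratios, not raw counts, across months. State how a month with no doses taken is handled, since the first two ratios are then undefined.

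State two limits beside the table. A shortfall of records against the pill count can be technical failure as well as non-use; where the transmission-error annotations of Protocol section IX are available, show those doses separately. Pill counts depend on unused pills being returned: a pill not brought back counts as taken, which raises apparent adherence and lowers apparent engagement.

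The cost is one extra table from data already collected, with no new visits or participants. Participant-level ratios will be somewhat noisier than pooled counts at N=15, so show the individual values alongside any summary.
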